7.7 EXTENT OF EXPOSURE

A descriptive statistics table with mean, SD, median and range of the number of days a patient was on treatment will be provided for the treated set. The tables will also provide the sum of the total time (in years) that all patients pooled together were on each treatment.

A separate listing will be created of any patients that switched treatment at any time indicating exposure to each treatment.

A frequency table of number and percent of patients belonging to each categorical range of exposure weeks will be provided:

> 0 to 1 week, > 1 to 4 weeks, > 4 to 8 weeks, > 8 to 16 weeks, > 16 to 24 weeks, > 24 to 28 weeks, > 28 weeks. Note that "> 1 to 4 weeks" stands for 8 to 28 days.

In addition, the following exposure cumulative categories will be provided:

≥1 day, ≥1 week, ≥4 weeks, ≥8 weeks, ≥16 weeks, ≥24 weeks, ≥28 weeks. Note that "≥1 week" category refers to 7 days.

7.8 SAFETY ANALYSIS

All safety analyses will be performed on the treated set, except one hypoglycaemia analysis that will also be performed on the FAS for a sensitivity purpose (refer to [Section 7.8.1.5](#)).

7.8.1 Adverse events

AEs will be coded using the latest version of the MedDRA coding dictionary at database lock.

Any clinically significant new finding in the physical examination, vital signs (pulse symptoms) and in the 12-lead ECG starting after visit 6 (randomisation visit) will be considered as an AE and will be reported as such.

Unless otherwise specified (refer to [Section 7.8.1.4](#) for analysis on number of hypoglycaemia events, and respectively to Section 7.8.1.5 for analysis on number of DKA events) the analyses of adverse events will be descriptive in nature and analyses of AEs will be based on the number of patients with AEs (not the number of AEs).

For analysis of AE attributes such as duration, severity, etc. multiple AE occurrence data on the CRF, will be collapsed into AE episodes provided that all of the following applies:

- The same MedDRA lowest level term was reported for the occurrences.
- The occurrences were time-overlapping or time-adjacent (time-adjacency of 2 occurrences is given if the second occurrence started on the same day or on the day after the end of the first occurrence).
- In addition certain analyses (other than the general analyses by SOC and PT produced by the XAE macro) will have their own collapsing rules. This concerns the following endpoints:
 - Genital infection events will not be collapsed if they are representative of different types (i.e. fungal balanitis or vulvovaginitis versus other than fungal balanitis or vulvovaginitis);

- Sepsis events will not be collapsed if they are representative of different sources of infection (i.e. urinary tract (urosepsis) versus other than urinary tract);
- Severe hypoglycaemia endpoint confirmed by adjudication will not be collapsed;
- Hypoglycaemia adverse events will not be collapsed (except in case of occurrences with identical onset date, time and glucose value);
- Lower limb amputation endpoint will not be collapsed
- Treatment did not change between the onset of the occurrences OR treatment changed between the onset of the occurrences, but no deterioration was observed for the later occurrence.

For further details on summarization of AE data, please refer to [\(8\)](#).

7.8.1.1 Assignment of AEs to treatment

In general, the analysis of adverse events will be based on the concept of treatment emergent adverse events. Exceptions are: malignancy events, bone fractures and lower limb amputation (see below). This means that all adverse events occurring between first drug intake until 7 days after last drug intake will be assigned to the randomised treatment. All adverse events occurring before first drug intake will be assigned to 'screening' and all adverse events occurring after last drug intake + 7 days will be assigned to 'post-treatment'. For details on the treatment definition, see [Section 6.1](#).

Malignancy, bone fracture and lower limb amputation events

For malignancy (and respectively bone fracture and lower limb amputation), in addition to the standard '7-day-on-treatment approach' detailed above, all malignancy adverse events (respectively bone fracture and lower limb amputation adverse events) that occurred between first study drug intake up to the trial termination date, will be pooled and analysed together in Section 15 of the trial report.

In general, in-text AE tables will only present AEs assigned to the randomised treatment taken except drug-related AEs which will also be presented as actual treatment taken at each given timepoint. Appendix 16.1.9.2 will display in addition AEs observed 'pre-treatment' (including AEs observed during screening, T1DM therapy optimisation and placebo run-in regardless of treatment group). In particular, summaries will be created to include an analysis where AEs and SAEs are assigned to the following phases: Screening, each treatment group, and post-treatment for each treatment group.

7.8.1.2 Analysis of other significant AEs

Other significant AEs will be reported and summarised according to ICH E3 criterion. Thus, AEs classified as 'other significant' will include those non-serious and non-significant adverse events with:

- 'action taken = discontinuation' or 'action taken = reduced', or

- Marked haematological and other lab abnormalities or lead to significant concomitant therapy as identified by the Clinical Monitor/Investigator at a Medical Quality Review meeting or Blinded Report Planning Meeting.

7.8.1.3 AE summaries

An overall summary of adverse events will be presented.

The frequency of patients with adverse events will be summarised by treatment, primary system organ class and preferred term. AEs will also be reported by intensity. Separate tables will be provided for patients with other significant adverse events according to ICH E3 (9), for patients with adverse events of special interest (AESI), for patients with serious adverse events, for patients with AEs leading to discontinuation, and for patients with drug-related AEs.

The system organ classes will be sorted according to the standard sort order specified by EMA, preferred terms will be sorted by frequency (within system organ class).

Appendix 16.1.9.2 will include the following analyses:

- an analysis on patients with adverse events by outcome,
- an analysis on the frequency of patients with non-serious adverse events occurring with incidence in preferred term greater than 5 % by treatment for disclosure on clinicaltrials.gov website.

The following analyses will also be reported in Appendix 16.1.9.2 for disclosure on EudraCT:

- AEs per treatment arm

This analysis includes the number of patients with serious AEs, the number of patients with non-serious AEs >5%, the total number of deaths (all causes), as well as the total number of deaths resulting from drug-related adverse events.

- Number of patients with non-serious AEs > 5% within any treatment arm, for each preferred term (grouped by standard SOC terms)
- Number of patients with serious AEs on preferred term level (grouped by standard SOC terms)

7.8.1.4 AEs of special interest (AESI)

The protocol defines the following adverse events that for analysis purposes will be considered as AESIs:

- Decreased renal function
- Hepatic injury
- Ketoacidosis
- Severe hypoglycaemia (i.e. severe hypoglycaemic episodes as defined in the CTP)
- Lower limb amputation

Events of these AESIs are identified through the AE being flagged by the investigator as an AESI on the case report form (CRF). For further details on the definition of these events, refer to Section 5.3.6.1 of the CTP.

The AESI decreased renal function will be summarised by SOC and PT based on the following narrow SMQ:

Renal:

- Acute renal failure: 20000003 (narrow SMQ)

This display will be replicated to present serious events and then events leading to discontinuation.

The acute renal kidney injury will also be discussed based on the creatinine laboratory data increase as detailed in [Section 7.8.2.4](#).

The AESI hepatic event will be summarised by SOC and PT based on the following narrow SMQs:

Hepatic:

- Liver related investigations, signs and symptoms: 20000008 (narrow SMQ)
- Cholestasis and jaundice of hepatic origin: 20000009 (narrow SMQ)
- Hepatitis, non-infectious: 20000010 (narrow SMQ)
- Hepatic failure, fibrosis and cirrhosis and other liver damage-related conditions: 20000013 (narrow SMQ)

This display will be replicated to present serious events and then events leading to discontinuation. A final display will summarise the AEs related to hepatic injury that occurred from baseline up to 30 days after the last dose of study medication.

Further laboratory analyses will support the hepatic evaluation. See [Section 7.8.2.2](#) for further details on elevated liver enzyme analyses.

Ketoacidosis:

- CEC confirmed ketoacidosis and ketosis endpoints
 - Analysis of number of patients with ketoacidosis

A frequency table will first summarize the results of the CEC adjudication committee for ketoacidosis events (refer to [Section 7.8.1.6](#) for further details on the adjudication process). This summary will present the number of patients with CEC confirmed certain ketoacidosis, potential ketoacidosis, unlikely ketoacidosis, unlikely ketoacidosis but ketosis, or unclassifiable events, by worst severity and requirement of hospitalisation.

A second frequency analysis will be created and will display the characteristics of ketoacidosis for patients with CEC certain ketoacidosis. These characteristics will include outcome, severity of the worst episode, time to onset of first episode, and lowest blood pH. This analysis will be successively repeated for ketoacidosis endpoints considered by the CEC as potential, as well as for ketoacidosis endpoints considered by the CEC as certain or potential.

Time to onset of the first CEC certain ketoacidosis event will be analysed by Kaplan-Meier estimates. The onset date determined by the adjudication committee will be used as date of event. The time to the occurrence of the event will be computed as date of the event minus date of first drug intake plus one day.

The Kaplan-Meier graph will present data up to the end of the treatment period.

Patient without an event will be considered censored at the date of the last trial drug intake plus seven day.

A log-rank test will be then computed to test the equality of the survival curves.

The Kaplan-Meier analysis and the log-rank test will then be performed for CEC certain or potential ketoacidosis event.

Frequency of patients with CEC certain ketoacidosis (and respectively CEC potential ketoacidosis) will be planned by preferred term from the specified trigger search terms for DKA.

- Analysis of frequency of ketoacidosis episodes

An overview table will first summarize the results of the CEC adjudication committee on ketoacidosis episodes by worst severity.

The CEC certain ketoacidosis episodes will be tabulated by treatment and characteristics of ketoacidosis (e.g. outcome, severity, pre-existing factors, blood pH).

When appropriate, the number of episodes per 100 patient-years will be calculated in addition to the number of episodes according to the following formula:

$100 * (\text{number of ketoacidosis events} / \text{time at risk [patient-years]})$ to report a diabetic ketoacidosis event)

Where time at risk [patient-years] is calculated as time from first administration of study drug until last administration of study drug + 7 days, summed up over all patients per treatment group, and divided by 365.25.

The same ketoacidosis episode analysis will be presented for CEC potential ketoacidosis, as well as for CEC certain or potential ketoacidosis.

- Other ketoacidosis endpoints

Patients with investigator defined AESI ketoacidosis will be tabulated by event characteristics; as well as the number of investigator defined AESI ketoacidosis episodes.

Frequency of patients with investigator defined AESI ketoacidosis will in addition be tabulated by SOC and PT, as well as using specified trigger search terms for DKA.

- Ketosis endpoints

Additional analyses will be produced to assess the risk of ketosis. Patient with ketosis are patients with either:

- CEC unlikely ketoacidosis but ketosis, or

- Single or multiple BHB readings (i.e. capillary patient-self measures or serum measurements) between >1.5 and < 3.8 mmol/L without accompanying typical ketoacidosis symptoms, hospitalisation or serious adverse event. As documented in the DKA CEC charter, these types of events are not considered trigger events for the adjudication

The number of patients with any ketosis events will be summarised as well as the number of ketosis episodes.

Ketosis episodes are defined as:

- CEC unlikely ketoacidosis but ketosis, or
- Single or multiple consecutive BHB readings >1.5 (i.e. capillary patient-self measures or serum measurements, within 24 hours of the previous reading for consecutive measurements) that do not trigger adjudication and that are not followed by an event triggering adjudication within 24 hours.

Severe hypoglycaemia adverse events:

In this section, only severe hypoglycaemia reported by the investigators as AESI, or severe hypoglycaemia that have been confirmed by the adjudication committee will be considered. Also note that 'CEC confirmed severe hypoglycaemia' refers to the exact same endpoint as 'severe hypoglycaemia confirmed by adjudication' that was the terminology used in the efficacy section.

Refer to [Section 9.3](#) for further details on the derivation of the severe hypoglycaemia adverse event endpoints analysed in this section.

- CEC confirmed severe hypoglycaemia endpoint
 - Analysis of number of patients with severe hypoglycaemia adverse event

A frequency table will first summarize the results of the adjudication committee on hypoglycaemic events that had been sent to the CEC for adjudication.

Kaplan-Meier graphs will be plotted for the time to first onset of CEC confirmed severe hypoglycaemia. The onset date determined by the adjudication committee will be used as date of event. The time to the occurrence of the event will be computed as date of the event minus date of first drug intake plus one day.

The Kaplan-Meier graph will present data up to the end of the treatment period.

Patient without an event will be considered censored at the date of the last trial drug intake plus one day.

A log-rank test will be computed to test the equality of the survival curves.

Patients with CEC confirmed severe hypoglycaemia will be tabulated by treatment and characteristics of hypoglycaemia including minimum glucose level and time to onset of first episode. The frequency of severe nocturnal hypoglycaemia AE (i.e. any hypoglycaemia event with an onset from 0:00 midnight to 5:59 a.m.) will also be evaluated as part of these characteristics.

Finally, the severe hypoglycaemia considered serious or requiring third person assistance will be tabulated using the narrow SMQ Hypoglycaemia. This analysis will be restricted to patients with CEC confirmed severe hypoglycaemia.

- Analysis of frequency of hypoglycaemia adverse events

The number of CEC confirmed severe hypoglycaemic episodes will be first tabulated by treatment and characteristics of hypoglycaemia. When appropriate, the number of episodes per patient-year will be provided in this analysis. The time at risk for severe hypoglycaemia [patient-years] will be derived similarly as for ketoacidosis, but in using 1 day of washout instead of 7 days in the calculation.

A negative binomial model will be fitted to analyse the event rate of CEC confirmed severe hypoglycaemia per patient-years, with terms for treatment, continuous baseline rate, continuous baseline HbA1c, continuous baseline eGFR (CKD-EPI, creatinine) and pre-existing insulin therapy as fixed effects and log(time at risk) as an offset.

In addition, the severe hypoglycaemic episodes that have been confirmed by the adjudication committee will be represented on a graph by hour of the day (from midnight to 11:59 pm).

- Investigator defined AESI severe hypoglycaemia adverse event endpoint

Patients with investigator defined AESI severe hypoglycaemia will also be summarised by treatment and event characteristics, as well as the investigator defined AESI severe hypoglycaemic episodes.

Patients with investigator defined AESI severe hypoglycaemia will additionally be summarised by SOC, PT and treatment group.

Lower limb amputation

A frequency table summarising the investigator defined AESI lower limb amputation events will be created by SOC and PT. The table will be then repeated for serious events, and for events leading to treatment discontinuation.

Patients with events detected based on project-defined preferred term lists for respectively vascular AEs, wound/infections, diabetic foot related AEs, nervous system disorders and volume depletion will be additionally summarised. All PTs associated to these events occurring before (\leq) the lower limb amputation procedure will be included in this analysis.

Finally, the characteristics of the lower limb amputation procedures (associated to the investigator defined AE) will be summarised. The reasons of the amputation and the level of the amputation will be the main characteristics of interest. All procedures that occurred between first study drug intake up to the later between the trial termination and the last AE onset date will be summarised.

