Clinical Trial Protocol

	Document Number:	c02993089-03
EudraCT No.:	2014-005256-26	
BI Trial No.:	1245.72	
BI Investigational Product:	Empagliflozin	
Title:	A Phase III, randomised, double blin parallel group, efficacy, safety and to oral doses of Empagliflozin as Adjur 26 weeks in patients with Type 1 Dia	plerability trial of once daily, active to inSulin thErapy over
Brief Title:	Empagliflozin as Adjunctive to InSu patients with Type 1 Diabetes Mellit	- ·
Clinical Phase:	III	
Trial Clinical Monitor:	Phone: Fax:	
Coordinating Investigator:	Phone: , Fax:	
Status:	Final Protocol (Revised Protocol bas	ed on Global Amendment 1)
Version and Date:	Version: 2.0	Date: 21 Oct 2016
	Page 1 of 122	

Proprietary confidential information.

© 2016 Boehringer Ingelheim International GmbH or one or more of its affiliated companies. All rights reserved. This document may not - in full or in part - be passed on, reproduced, published or otherwise used without prior written permission.

Trial Protocol Version 2.0 Page 2 of 122

Proprietary confidential information © 2016 Boehringer Ingelheim International GmbH or one or more of its affiliated companies

CLINICAL TRIAL PROTOCOL SYNOPSIS

Name of company:		Boehringer Ingelheim					
Name of finished prod	uct:						
Name of active ingredi	ent:	Empagliflozin					
Protocol date:	Trial number:		Revision date:				
14 Jul 2015	1245.72		21 Oct 2016				
Title of trial:	safety and tolerability	ed, double blind, placebo-controlled trial of once daily, oral doses of Er er 26 weeks in patients with Type 1	npagliflozin as Adjunctive				
Coordinating Investigator:	Phone:						
Trial sites:	Multi-centre trial plan	ned to be conducted in multiple cou	ıntries				
Clinical phase:	III	•					
Objectives: Methodology:	The objective of this study is to assess the efficacy, safety, tolerability and pharmacokinetics (PK) of once daily oral doses of empagliflozin 2.5 mg, 10 mg and 25 mg compared to placebo in patients with Type 1 diabetes mellitus (T1DM) as adjunctive to insulin therapy Randomised, double-blind, placebo-controlled parallel group comparison of 3 oral once daily doses (2.5 mg, 10 mg and 25 mg) of empagliflozin to placebo. Randomisation will be stratified by:						

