Trial Protocol Version 2.0

Page 110 of 122

	 "baseline" refers to the 2 week placebo run-in period throughout this protocol (1 week of evaluable data required). Change from baseline in the percentage of time spent in target glucose range of 70-180 mg/dL (3.9-10.0 mmol/L) as determined by CGM in Week 25 to 26 Change from baseline in interstitial glucose variability (inter quartile range, IQR) as determined by CGM in Week 25 to 26
	Change from baseline in AUC for interstitial glucose (mmol/24 hour, average from evaluable data from CGM period, minimum of 1 week required) in Week 25 to 26"
	Has been removed
Rationale for change	Exploratory secondary endpoints moved from secondary endpoints to further endpoints to align with project standards
Section to be changed	
Description of change	

c02993089-03 Trial Protocol Version 2.0 Page 111 of 122

Proprietary confidential information © 2016 Boehringer Ingelheim International GmbH or one or more of its affiliated companies

Rationale for change	
Rationale for change	
Section to be abanged	5.3.2.2 Ketone measurement
Section to be changed Description of change	"Regular (e.g. 2-3 weekly) measurements before
Description of change	breakfast are recommended throughout the trial as
	from Visit 2. More frequent (e.g. once daily)
	measurements before breakfast are recommended
	during the run-in phase and during the first 4 weeks
	of the treatment phase and might also be agreed upon with the patient afterwards if deemed necessary
	by the Investigator."
	Has been changed to:
	"Regular (e.g. 2-3 times a week) measurements
	before breakfast are recommended throughout the

	trial as from Visit 2. More frequent (e.g. once daily) measurements before breakfast are recommended during the run-in period and during the first 4 weeks of the treatment period and might also be agreed upon with the patient afterwards if deemed necessary by the Investigator."
Rationale for change	Clarification
Cartina to be all	5261 Definitions of AE
Section to be changed	5.3.6.1 Definitions of AEs
Description of change	Added to Adverse events of Special Interest (AESIs):
	"Events involving lower limb amputation
	This definition includes amputation (i.e. resection of a limb through a bone), disarticulation (i.e. resection of a limb through a joint) and auto-amputations (i.e. spontaneous separation of non-viable portion of the lower limb).

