	Not included in this definition are debridement (removal of callus or dead tissue), procedures on a stump (like stump revision, drainage of an abscess, wound revision etc.) and other procedures (e.g., nail resection or removal) without a concomitant resection of a limb (amputation or disarticulation).
	Each lower limb amputation, disarticulation, or auto- amputation should be reported separately. The SAE report should include the date of the procedure, the level of amputation or disarticulation, the medical condition(s) leading to the procedure and if the patient had some of the known risk factor(s) for lower limb amputation."
Rationale for change	To meet new regulatory requirements
Section to be changed	

Define le female sur	Comment of the state of the sta
Rationale for change	Correction of error/omission
Section to be changed	Multiple sections
Description of change	6.2.1.1 Screening visit (Visit 1) 6.2.1.2 T1DM therapy optimisation period (Visits 2, 3 and 4T)

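### Lower limb amputations that preceded Amendment 1 may be missing from the dedicated amputation tables, because SAP 7.8.1.4 relies on the investigator's AESI flag with no visible term search behind it

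*SAP*

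**What the plan says.** **Protocol.** The synopsis dates the protocol 14 Jul 2015. The title page of Version 2.0 carries "Date: 21 Oct 2016". Section 11 records that Amendment 1 put events involving lower limb amputation on the AESI list in 5.3.6.1 ("Added to Adverse events of Special Interest (AESIs")), with the reason "To meet new regulatory requirements". The current 5.3.6.1 counts amputation, disarticulation and auto-amputation, and excludes debridement, stump procedures and similar interventions. Section 5.3.7 requires all adverse events to be collected from consent to trial completion, whether or not they are AESIs.

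**SAP 7.8.1.4.** Lower limb amputation is one of five listed AESIs, and the rule for all five is: "Events of these AESIs are identified through the AE being flagged by the investigator as an AESI on the case report form (CRF"). For amputation the section adds:
- "A frequency table summarising the investigator defined AESI lower limb amputation events will be created by SOC and PT", repeated for serious events and for events leading to discontinuation;
- a summary of related conditions up to the procedure: "Patients with events detected based on project-defined preferred term lists for respectively vascular AEs, wound/infections, diabetic foot related AEs" and others;
- "the characteristics of the lower limb amputation procedures (associated to the investigator defined AE) will be summarised".

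**SAP 7.8.1.1.** "For malignancy (and respectively bone fracture and lower limb amputation), in addition to the standard '7-day-on-treatment approach' detailed above", all such events from first drug intake to trial termination are also pooled and analysed. There is no cut at the amendment date, and no separate rule for finding the events.

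**The concern.** The flag depends on the investigator treating amputation as an AESI. Before Amendment 1 reached a site, the protocol gave no instruction to do so. An amputation in that period would be recorded as an ordinary adverse event, serious or not. Unless someone returned to it and set the flag, a program that follows SAP 7.8.1.4 would not select it.

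The event would then drop out of the frequency table and its serious and discontinuation repeats. It would also drop out of the summary of preceding conditions, which starts from an identified amputation, and out of the procedure table. Yet the pooled analysis in SAP 7.8.1.1 would be read as covering every patient from first dose. At stake is a possible undercount of a rare event on a question that was added for regulatory reasons.

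**Working it through.** The plan states no figure on this point, so there is none to reproduce. The check compares the text and then does some date arithmetic.

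**1. How each event of this kind is found in the visible SAP**

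| Event | Means of identification besides the AESI flag | SAP section |
|---|---|---|
| Decreased renal function | Narrow SMQ | 7.8.1.4 |
| Hepatic injury | Four narrow SMQs | 7.8.1.4 |
| Ketoacidosis | Adjudication and trigger search terms | 7.8.1.4 |
| Severe hypoglycaemia | Adjudication | 7.8.1.4 |
| Bone fracture (not an AESI) | BIcMQ | 7.8.1.5 |
| Malignancy (not an AESI) | Sub-SMQs | 7.8.1.5 |
| Lower limb amputation | None visible | 7.8.1.4 |

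The preferred-term lists in the amputation text cover vascular, wound and infection, diabetic foot, nervous system and volume depletion events. They describe what came before an amputation and do not find amputations. SAP 7.8.1.1 groups malignancy, fracture and amputation for follow-up to trial termination, and amputation is the only one of the three without a visible search.

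**2. Time before the amendment**

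14 Jul 2015 to 21 Oct 2016 is 465 days, or 465/7 = 66.4 weeks. This bounds the calendar period, not the patient time, because neither document gives the first or last randomisation date or the date each site implemented the amendment.

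**3. Illustration only**

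Assumptions, none taken from the documents: randomisation is uniform from date F to date L, and every patient contributes 182 + 21 = 203 days (26 weeks of treatment plus 3 weeks of follow-up). F is 1 Oct 2015, 1 Jan 2016 or 1 Jun 2016. L is 21 Oct 2016, 1 Jan 2017 or 22 Mar 2017; the last is 203 days before the revised SAP of 11 Oct 2017.

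For a patient randomised on day d, the time before a cut date c is max(0, min(203, c − d)). The share is the sum of this over d from F to L, divided by 203 × (number of days from F to L inclusive).

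Example, F = 1 Jun 2016 and L = 22 Mar 2017: there are 295 randomisation days. Those before the cut contribute 142 + 141 + … + 1 = 142 × 143/2 = 10,153 days. The share is 10,153/(203 × 295) = 10,153/59,885 = 17%.

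| First randomised | Last randomised | Share before 21 Oct 2016 | Share if sites implemented 90 days later |
|---|---|---|---|
| 1 Oct 2015 | 21 Oct 2016 | 74% | 92% |
| 1 Oct 2015 | 1 Jan 2017 | 62% | 82% |
| 1 Oct 2015 | 22 Mar 2017 | 53% | 70% |
| 1 Jan 2016 | 21 Oct 2016 | 65% | 89% |
| 1 Jan 2016 | 1 Jan 2017 | 53% | 77% |
| 1 Jan 2016 | 22 Mar 2017 | 43% | 63% |
| 1 Jun 2016 | 21 Oct 2016 | 35% | 78% |
| 1 Jun 2016 | 1 Jan 2017 | 23% | 61% |
| 1 Jun 2016 | 22 Mar 2017 | 17% | 44% |

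The range, 17% to 74% (44% to 92% with the lag), is driven by the assumed dates. It measures patient time, not missed events. The documents give no amputation rate, so an expected number of missed events cannot be computed and may be zero.

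**The case against.** A reader might infer that earlier amputations are certain to be left out of the trial's tables. The documents do not support that.

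- **The events stay visible elsewhere.** All adverse events are collected whatever their flag (protocol 5.3.7). SAP 7.8.1.3 tabulates all of them by system organ class and preferred term, with separate tables for serious events. This stands. It limits the gap to the dedicated tables, but the general tables do not apply the protocol's amputation definition and may spread cases over several preferred terms.
- **Retrospective flagging is not excluded.** SAP 7.8.1.4 says how events are identified at analysis, not when the flag had to be set. This stands, but the visible text does not say that it was done either.
- **The flag may not govern everything.** SAP 7.8.1.1 speaks of amputation adverse events without naming a flag, and the procedure table refers to the investigator-defined AE, not AESI. The text is therefore ambiguous for those two analyses. The frequency table and its repeats are explicitly limited to the investigator-defined AESI.
- **A search list may be redacted.** Much of SAP section 9 is blacked out, so this is possible. However, the amputation text refers to no such list, whereas the severe hypoglycaemia text does point to section 9.3.
- **There is no evident bias between arms.** The trial is double-blind with 1:1:1:1 allocation, and the safety analyses are mostly descriptive, without planned hypothesis tests (protocol 7.3.4). Missed flags should not depend on treatment. This stands: the problem is a possible undercount. With a rare event, one missed case could still alter how the arms look side by side, but the documents do not show that any conclusion would change.

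**Conclusion.** The concern holds in a limited form. Amputation became an AESI only with Amendment 1. The dedicated tables rest on investigator-defined events, and among the AESIs amputation is the only one without a visible term search or adjudication as a backstop. Followed as written, the plan may omit amputations that occurred before a site implemented the amendment, unless they were flagged retrospectively.

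The size cannot be derived from the documents: enrolment dates, site implementation dates and the number of amputations are all absent. The percentages show only that the affected patient time need not be small. They should not be read as a share of events lost.

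The conclusion assumes that no amputation search is hidden in the redacted text and that no retrospective review was made. If either exists, a sentence saying so would close the point. Otherwise this is an inexpensive improvement that should be made.

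**What to change.** In SAP 7.8.1.4, define a lower limb amputation as any event that either carries the investigator's AESI flag or is found by a pre-specified preferred-term search of all adverse events and recorded procedures. The search should cover amputation, disarticulation and auto-amputation as defined in protocol 5.3.6.1. Confirm the hits by blinded review, apply the rule from first drug intake to trial termination for every patient, and run all the amputation tables on the resulting set. Separate columns for flagged and search-found events are optional.

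The cost is a sentence in the SAP, a term list and a short blinded review of data already collected. The small downside is that events from before the amendment may lack details such as amputation level or risk factors, which would be shown as missing in the procedure table.
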